The main objective of the study is to identify the optimal ablation strategy for suppression of persistent AF.

The secondary objectives of the study are:

- To define the local myocardial image characteristics of slow conduction AF substrates.
- To define the local myocardial structural changes post ablation that associate with AF suppression at 1-year follow-up
- To compare cardiac remodeling and atrial function at 1-year follow-up between PVI only and tailored catheter ablation groups

3. Background

Atrial fibrillation (AF) is associated with increased risk for mortality, heart failure, and thromboembolic events, and has a worldwide prevalence of >33.5 million (Benjamin et al., 1998; Chugh et al., 2014; Estes et al., 2011; Schnabel et al., 2015). Catheter ablation of AF is evolving as an effective therapy for symptomatic AF (Calkins et al., 2012). Recurrent AF after ablation, however, remains a problem and has been reported to associate with the baseline extent of left atrial (LA) late gadolinium enhancement (LGE) on cardiac magnetic resonance (CMR) (Marrouche et al., 2014; McGann et al., 2014). Mechanistically, persistent AF appears to be more reliant upon fibroblast proliferation and myocyte-fibroblast coupling than paroxysmal AF, which is primarily dependent upon pulmonary vein triggers (Haissaguerre et al., 1998; Inoue et al., 2012; Wilber, 2012). Therefore, we hypothesize that the substrate for persistent AF is detectable on atrial LGE-CMR and variable among patients, and that the substrate predicts patient outcomes after anatomic non-tailored ablation, and is more likely to respond to individually tailored ablation approaches. Two individually tailored approaches will be studied including empiric targeting of dense LGE, confirmed on bipolar mapping to have voltage <0.1 mV, and modeling based targeting of rotor anchor sites.

4. Study Procedures

a. Study Design

Initially, we propose prospective enrollment of 30 participants with persistent AF. Patients presenting to our institution who meet the inclusion criteria will be asked to participate in the study. All patients will undergo routine clinical care including echocardiography as indicated.

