All patients will undergo a LGE-MRI within 30 days prior to the ablation procedure. The clinical purpose of the initial MRI is to define the anatomy of the heart chambers as well as the vessels for procedure planning. For research purposes, we will use this initial clinical MRI to delineate atrial structural remodeling or fibrosis to be used during the procedure in patients randomized to group 2 (pulmonary vein isolation + scar-based ablation) and for later analysis in all patients.

Imaging is done at our institution and will be reviewed for quality by the study staff. LGE-MRI sequences that do not meet quality standards for fibrosis analysis will not be further processed and these patients will be excluded from the study. Subjects for whom images are successfully evaluated will be randomized to the study groups.

This will be followed by block randomization in 1:1:1 format to a) pulmonary vein isolation (PVI) only (current standard of care), b) PVI plus targeting of dense LGE sites, which are confirmed on bipolar mapping to have voltage <0.1 mV, and c) PVI plus targeting of rotor anchor sites predicted by modeling.

At baseline, all patients will be evaluated for their quality of life (QOL) using the Short-form health survey (SF-36) (Ware & Sherbourne, 1992) for overall as well as AF-related impact on quality of life (Refer to additional study documents). The severity of symptoms will be tested using the European Heart Rhythm Association (EHRA) score of atrial fibrillation and the Canadian Cardiovascular Society (the CCS-SAF) scale (Dorian et al., 2006). Clinical data will be stored electronically and linked to a specific research ID number. Information linking de-identified data to the patients will be stored in the locked research office, in a password-protected file. Only members of the research team, in charge of collecting clinical information, will have access to this file. Individual subject binders containing signed consent forms and clinical source documentation will be labeled using study subject numbers and stored in the locked research office mentioned previously.

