Patients undergoing MRI angiogram are routinely injected with gadolinium as contrast. Gadolinium-based MRI contrast agents are used to visualize scar/ablation lesions in the atrial wall (McGann et al., 2014). Gadolinium chelates used as intravenous contrast media are extremely safe in patients with normal kidney function and do not exhibit the nephrotoxicity associated with iodinated media. Minor reactions including nausea and hives may occur in a small percentage of cases. Severe anaphylactic reactions are extremely uncommon (Runge, 2001).

- b. Justification and safety information if FDA approved drugs will be administered for non-FDA approved indications or if doses or routes of administration or participant populations are changed.

Gadolinium (total dose of 0.2 mmol/kg) will be administered 10 minutes prior to delayed enhancement imaging to evaluate for the presence of myocardial scar. Gadolinium-based contrast agents are not FDA-approved for diagnosis of cardiac disease by MRI. However, these agents have been routinely used for more than 10 years at the JHH and other centers for clinical and research purposes to evaluate diseases of the myocardium and vessels (Akoum & Marrouche, 2014) (Zareian et al., 2015). The standard gadolinium dose at JHH and other institutions in cardiac MRIs is a maximum of 0.2 mmol/kg.

- c. Justification and safety information if non-FDA approved drugs without an IND will be administered. N/A

7. Study Statistics

- a. Primary outcome variable.

Data from AliveCor® Mobile ECG rhythm device recordings, follow-up visits (examinations and ECGs), and QOL/follow-up questionnaires will be used to identify the success rates of the procedure. Procedure failure is defined as symptomatic or asymptomatic AF/Atrial flutter/Atrial tachycardia of at least 30 seconds duration that is documented by an ECG or device recording system, occurring after the 3-month blanking period following catheter ablation. Individually tailored ablation strategies for suppression of persistent AF have not been investigated. We hypothesize that individually tailored ablation strategies will improve AF/AT suppression compared to PVI alone. The association of time to AF/AT recurrence with ablation strategy will be examined in 30 randomized patients.

- b. Secondary outcome variables.

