During ablation, the spatial coordinates and electrogram characteristics of >200 intra-cardiac points are sequentially sampled and saved. We hypothesize that sites with slow conduction during sinus rhythm,

representing AF substrates, are detectable as sectors with intermediate LGE intensity [image intensity ratio (IIR) 0.9-1.6] on LGE-CMR. We will co-register the spatial coordinates of sites exhibiting slow conduction with pre-procedural LGE-CMR for 30 patients. We will then compare the baseline image intensity ratio of sites with slow conduction versus other sites.

Catheter ablation results in long-term AF suppression in approximately 50% of patients with persistent AF. We hypothesize that AF suppression at 1-year will be associated with the presence of IIR>1.6 at the 1-year LGE-CMR in sectors where slow conduction was observed at baseline. We will co-register the baseline spatial coordinates of sites exhibiting slow conduction with 1-year post-procedural LGE-CMR images for 30 patients randomized to ablation. We will then compare the 1-year image characteristics of sectors with slow conduction among patients with and without AF suppression at 1-year follow-up.

Catheter ablation promotes scar formation and more extensive ablation strategies may adversely affect left atrial function. However, AF recurrences and continuation of antiarrhythmic drug therapy may also lead to progression of atrial and ventricular dysfunction. We hypothesize that more extensive patient tailored approaches will have less negative impact on atrial and overall cardiac function. We will measure the change (baseline to 1-year MRI) in left atrial and left ventricular regional and global strain in 30 randomized patients. We will then examine the association of the change in regional and global strain with ablation strategy.

- c. Statistical plan including sample size justification and interim data analysis.

Based on the variable success rate of 40-80% in AF ablation, we anticipate that the study cohort of 30 patients would produce adequate sample size in all treatment arms and be sufficient to make meaningful statistical comparison.

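### The 1-year scar comparison in Section 7b pools the three arms without randomised arm in the analysis, so an association it finds may partly be the arm effect

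*Combined protocol and SAP*

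**What the plan says.** Section 2 sets the objective: "To define the local myocardial structural changes post ablation that associate with AF suppression at 1-year follow-up". Section 7b turns it into a hypothesis about the sectors found to conduct slowly before ablation: "AF suppression at 1-year will be associated with the presence of IIR>1.6 at the 1-year LGE-CMR in sectors where slow conduction was observed". The data are "1-year post-procedural LGE-CMR images for 30 patients randomized to ablation", that is, all three arms together, and the comparison is: "We will then compare the 1-year image characteristics of sectors with slow conduction among patients with and without AF suppression at 1-year follow-up".

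Four other statements bear on the role of arm:

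- Section 4a assigns patients using "block randomization in 1:1:1 format to a) pulmonary vein isolation (PVI) only (current standard of care), b) PVI plus targeting of dense LGE sites", and a third arm with PVI plus modelled rotor sites. The tailored arms therefore receive lesions beyond PVI.
- Section 7b, introducing the atrial-function outcome: "Catheter ablation promotes scar formation and more extensive ablation strategies may adversely affect left atrial function".
- Section 6a says that gadolinium-enhanced MRI shows ablation lesions as well as scar.
- Section 7a: "We hypothesize that individually tailored ablation strategies will improve AF/AT suppression compared to PVI alone".

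Section 7c does not bring arm into this comparison. Its chi-square and rank-sum tests are for differences between treatment groups, its t-test is for images before and after ablation, and its multivariable Cox model lists no covariates and yields hazard ratios. The strain analysis, which comes next in Section 7b, does name ablation strategy.

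**The concern.** The comparison sets scar in slow-conduction sectors against AF suppression. If the tailored arms have more scar in those sectors and also more suppression, suppressed patients come disproportionately from arms with more scar. A pooled difference then appears even when scar and suppression are unrelated inside every arm. An analyst who follows the text could not tell that difference from a within-arm link.

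There is a second, opposite cost. If arm changes scar but not suppression, no false association arises, but the scar differences between arms add noise and can hide a real within-arm association.

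**Working it through.** **Plan's own figure.** The plan states no power, effect size or sample size for this comparison, so there is nothing to reproduce beyond the total of 30 and the two-sided 5% level (Section 7c).

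**Inputs.** From the documents: 30 patients allocated 1:1:1, so about 10 per arm; overall suppression of about 50% (Section 7b); a success range of 40–80% (Sections 1 and 7c), which is not given as a contrast between arms. Assumed, because the documents give none: each patient's share of slow-conduction sectors with IIR>1.6 has mean 30/60/60% (PVI / tailored / tailored) and within-arm SD 20 points, with no link to suppression inside any arm.

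**Step 1: spurious gap.** With suppression p_k and mean scar m_k in arm k, the expected pooled difference is

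Σp_k·m_k / Σp_k − Σ(1−p_k)·m_k / Σ(1−p_k).

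- 40/55/55%: (12+33+33)/1.5 − (18+27+27)/1.5 = 52 − 48 = 4 points.
- 50/70/70%: (15+42+42)/1.9 − (15+18+18)/1.1 = 52.1 − 46.4 = 5.7 points.
- 40/80/80%: (12+48+48)/2.0 − (18+12+12)/1.0 = 54 − 42 = 12 points.

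**Step 2: approximate rejection rate.** The pooled SD includes the spread between arms: the means 30, 60, 60 average 50, so the between-arm variance is (400+100+100)/3 = 200 and the pooled SD is √(400+200) = 24.5. The standard error is 24.5·√(1/n₁+1/n₂), with n₁ and n₂ the expected numbers with and without suppression. The simulation columns come from trials of 3×10 patients.

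| Suppression | n₁/n₂ | Gap/SE | Normal approximation | Simulated, pooled t-test | Simulated, arm in model |
|---|---|---|---|---|---|
| 40/55/55% | 15/15 | 4/8.9 = 0.45 | 7% | about 7% | about 5% |
| 50/70/70% | 19/11 | 5.7/9.3 = 0.62 | 10% | about 10% | about 5% |
| 40/80/80% | 20/10 | 12/9.5 = 1.26 | 24% | about 25% | about 5% |

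The rank-sum test gives 9% in the middle row. With a smaller scar contrast, 30/45/45%, and suppression 40/55/55%, the pooled rate is about 6%.

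**Step 3: the same with a yes/no scar variable.** Take IIR>1.6 present in 30/70/70% and suppression 40/80/80%. Scar is then present in (0.12+0.56+0.56)/2.0 = 62% of suppressed patients and (0.18+0.14+0.14)/1.0 = 46% of the others. The pooled odds ratio is (0.62/0.38)/(0.46/0.54) = 1.92, against 1 inside every arm. The pooled chi-square test rejects in 14% of trials and the arm-stratified Mantel-Haenszel test in about 5%. With suppression 40/55/55% the odds ratio is 1.24 and the pooled rate 6%. If arm affects only scar or only suppression, the odds ratio is 1.00 and the rate 5%.

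**Step 4: power.**

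- Equal suppression in all arms, scar 30/60/60%, and a real 20-point within-arm difference: power is 53–56% ignoring arm and 67–72% with arm.
- The same real difference, but no scar difference between arms: 74% ignoring arm and 71% with arm.
- Scar as the pathway, so that suppression depends only on scar (logistic slope 0.04 or 0.05 per point, assumed): about 64% pooled against 44% adjusted, and about 80% against 57%.

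**The case against.** A reader might infer that arm is known to drive both variables, so that any association found would be only the arm effect. The documents do not support that. The effect of arm on suppression is the hypothesis under test. The scar at issue lies inside baseline slow-conduction sectors, which Section 7b expects to show intermediate enhancement (IIR 0.9–1.6), whereas the extra targets are dense enhancement with voltage below 0.1 mV or modelled rotor sites. Nothing says that the extra lesions fall on the slow-conduction sectors. If either link is absent, there is no artefact. This stands, and the point is worded accordingly.

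A reader might also infer that the pooled comparison should give way to the adjusted one. That goes too far. If the tailored lesions work by scarring these sectors, scar is a mediator. The difference between arms is then genuine signal, and adjustment discards it (last line of Step 4). This also stands, and it is why both estimates are needed.

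Two practical limits are fair too. With 80% suppression and 10 per arm, the chance that at least one tailored arm has no failures, and so contributes nothing within arm, is 1 − (1 − 0.8¹⁰)² = 20%. And this is a secondary objective, worded as association, in a study that collects preliminary data.

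None of this supplies the missing specification. The pooled comparison alone cannot separate a within-arm link from an arm effect, and the plan says nothing on how it would be read.

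**Conclusion.** The concern holds in a limited form. The comparison omits randomised arm, which on the plan's own hypotheses may affect both variables, so a pooled association may partly reflect the arm effect and cannot be read as a within-arm link.

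The size depends on scar rates and suppression rates by arm that the documents do not give. At 30 patients the inflation is slight (about 7%) when overall suppression matches the 50% in Section 7b. It becomes clear (25%) only when arm strongly affects both variables; the 40/80/80% case turns a range across AF populations into a contrast between arms, so it is an upper scenario and not an expectation.

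The artefact grows with sample size. At 3×100 patients with the same scar assumptions, the pooled test rejects in 30%, 49% and 98% of trials in the three scenarios, against about 5% with arm. The plan does not say that the intended 300-patient trial will use this analysis; the figures matter only if it is carried over.

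The change is worth making, but it does not touch the primary outcome.

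**What to change.** Add to Section 7b:

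> Using one value per patient, the comparison of 1-year image characteristics by AF suppression will be made in a linear model with randomised arm (3 levels) as a factor, or by an arm-stratified test. The arm-adjusted and pooled estimates will be reported side by side with confidence intervals and labelled exploratory. An association seen only in the pooled estimate will not be interpreted as separate from the arm effect.

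No new data are needed. The cost is 2 degrees of freedom, or about 3 points of power if the arms do not differ in scar. The adjusted test loses about 20 points if scar in these sectors is the pathway by which the tailored arms work; keeping the pooled estimate beside it covers that case.

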A pre-ablation cardiac MRI is clinically indicated to assess baseline cardiac anatomy prior to procedure. Routine and LGE protocols will be used to acquire MR images. All patients will be asked to undergo a repeat LGE-MRI 12 months after the ablation. This is done for research purposes. Renal function is routinely monitored prior to gadolinium-enhanced MRI as a standard of clinical care.

With regards to the ablation procedure, all patients will undergo AF ablation. The procedure consists of circumferential pulmonary vein lesions under electro-anatomical guidance using CARTO (Biosense Webster Inc., Diamond Bar, CA). Operators will use either a 3.5mm irrigated tip radiofrequency ablation catheter (ThermoCool SmartTouch, Biosense Webster Inc., Diamond Bar, CA) or a cryoballoon catheter (Arctic Front Advance, Medtronic Inc., Minneapolis, MN). This procedure is FDA approved and will be conducted in all treatment arms according to standard of care. However, patients in the second group will undergo additional targeting of dense LGE sites, confirmed on bipolar mapping to have voltage <0.1 mV and patients in the third group will undergo targeting of rotor anchor sites as predicted by computational modeling. A detailed protocol of rotor ablation is described in the literature and shows no added complications compared to the conventional procedure (Narayan et al., 2014).

To prevent short-term recurrence of AF, patients will be kept on anti-arrhythmic regimen for the first 1 to 3 months after the ablation to be discontinued thereafter in the absence of AF recurrence, at the discretion of the treating physician. In addition, standard protocols for anticoagulation prior to, during, and after the ablation procedure will be applied.

After the ablation, clinical follow-up visits are scheduled at 3, 6 and 12 months. Research follow-up questionnaires and 12-lead ECG recordings will be done at the same day of the visits. All patients will undergo rhythm monitoring to detect AF recurrence using a portable, smartphone operated, AliveCor® Mobile ECG device. The AliveCor® Mobile ECG is a mobile, clinical-quality electrocardiogram (ECG) recorder. The software application can store thousands of recordings on smartphones or tablets and these recordings are wirelessly transmitted to AliveCor, Inc. (AliveCor) servers accessible to authorized users including healthcare providers. This device will be provided to the patients at no cost after enrollment in the study.

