Comparison variables will be presented as means \pm SD, and categorical variables as numbers and percentages. Differences between treatment groups will be assessed using the Pearson Chi-square test and the Wilcoxon rank-sum test. Survival curves for time to event analysis will be estimated using the Kaplan-Meier method, and the differences between the curves will be tested for significance with the log-rank statistic. Weekly event rates will be calculated by dividing the event rate by the maximum follow-up period in each arm of the Kaplan-Meier analysis. Hazard ratios will be calculated by univariate and multivariate analysis using the Cox proportional-hazards regression model. When comparing MR image characteristics as well as LA function between pre and post-ablation imaging, the Student's t-test will be using for comparison of the means. All statistical testing will be 2-tailed. Results will be considered statistically significant at a level of $p < 0.05$.

- d. Early stopping rules. N/A

8. Risks

- a. Medical risks, listing all procedures, their major and minor risks and expected frequency.

As discussed above, all procedures except the post-ablation MRI is part of the standard clinical care. In addition, groups reporting their experience with substrate-based ablation have not encountered increased complications compared to the conventional ablation procedure (Narayan et al., 2012). In addition, there is no data suggesting any health hazard associated with magnetic field exposure (Schenck, 2000). All patients with pacemakers, implanted defibrillators or electronic/metallic devices, shrapnel and other metals such as metal in the eyes will be excluded.

Gadolinium chelates used as intravenous contrast media in MRI are considered safe and do not exhibit the nephrotoxicity associated with iodinated media. The injection of contrast intravenously is not painful, but

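### One-year strain is to be compared between arms on change from baseline with no baseline adjustment; ANCOVA on the same scans would usually be more precise at almost no cost

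*Combined protocol and SAP*

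**What the plan says.** All references are to the combined protocol and SAP.

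- **Section 2 (Objectives)** lists as a secondary objective: "To compare cardiac remodeling and atrial function at 1-year follow-up between PVI only and tailored catheter ablation groups".
- **Section 7b (Secondary outcome variables)** defines the outcome: "We will measure the change (baseline to 1-year MRI) in left atrial and left ventricular regional and global strain in 30 randomized patients". The analysis is one sentence: "We will then examine the association of the change in regional and global strain with ablation strategy". The same paragraph gives the reason for looking, namely that "more extensive ablation strategies may adversely affect left atrial function".
- **Section 7c (Statistical plan)** covers comparisons between arms in one sentence: "Differences between treatment groups will be assessed using the Pearson Chi-square test and the Wilcoxon rank-sum test". Chi-square does not fit continuous strain, which leaves the rank-sum test. For imaging before versus after ablation, a Student's "t-test will be using for comparison of the means"; pairing is not mentioned. The only multivariable model in the section is Cox regression, for hazard ratios.
- **Section 4a (Study Design)** allocates 1:1:1 and places randomisation after the baseline scan has been assessed: "Subjects for whom images are successfully evaluated will be randomized to the study groups". For follow-up, "All patients will be asked to undergo a repeat LGE-MRI 12 months after the ablation".

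Baseline strain is not used as a covariate anywhere in the document.

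**The concern.** When an outcome is measured before and after a randomised treatment, subtracting the baseline in full is efficient only if the two measurements are very highly correlated. Otherwise the change score carries baseline noise into the comparison. ANCOVA estimates how much of the baseline to remove.

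Three things are at stake.

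- **Precision.** There are about 10 patients per arm, and possibly fewer with a 1-year scan. This is also the secondary outcome for which section 7b itself raises a possible adverse effect of more extensive ablation.
- **Chance imbalance.** In small arms, baseline strain may differ between groups. Given such a difference, the change-score estimate is shifted by regression to the mean.
- **Usable output.** A rank-sum p-value supplies no adjusted difference with a confidence interval. Such an estimate is what a pilot can best hand on to the planned 300-patient trial. The rank-sum test also compares two groups, while the trial has three.

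**Working it through.** **Inputs from the documents.** 30 patients allocated 1:1:1, so about 10 per arm. PVI only against both tailored arms is therefore 10 v 20. Tests are two-sided at 0.05.

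**Inputs assumed.** The documents give no strain SD, effect size, power or baseline-to-1-year correlation (ρ). I take ρ = 0.3, 0.5, 0.7 and 0.9, normal data and equal SDs (σ) at both times. There is no strain sample-size figure to reproduce: section 7c justifies the 30 patients from ablation success rates only.

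**Step 1: variance by formula.** With k = 1/n₁ + 1/n₂:

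- Change score: σ² × 2(1 − ρ) × k
- ANCOVA: σ² × (1 − ρ²) × k × [1 + 1/(df − 2)], where df is the within-group degrees of freedom and the bracket is the price of estimating the slope
- Ratio, ANCOVA to change: (1 + ρ)/2 × [1 + 1/(df − 2)]

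For 10 v 20, df = 28 and the bracket is 1 + 1/26 = 1.038. The ratios are 0.65 × 1.038 = 0.675, 0.75 × 1.038 = 0.779, 0.85 × 1.038 = 0.883 and 0.95 × 1.038 = 0.987.

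In a three-arm model df = 27, the bracket is 1.04, and the ratios are 0.676, 0.780, 0.884 and 0.988. Dividing 30 by these, 30 patients analysed by ANCOVA are worth about 44, 38, 34 and 30 analysed on change. Break-even is at ρ = 2/1.04 − 1 = 0.923. At ρ = 0.95 the ratio is 0.975 × 1.04 = 1.014, a loss of about 1%.

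**Step 2: simulation** (20,000 replicates per cell). At 10 v 20 the simulated variance ratios are 0.681, 0.781, 0.885 and 0.989, in line with the formula. These are reductions of 31.9%, 21.9%, 11.5% and 1.1%. Rejection under the null is 0.047 to 0.054 for all methods, and change score and ANCOVA both recover the true difference on average.

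Power at 10 v 20 for a 0.8 SD difference, with mean 95% CI half-widths in SD units:

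| ρ | Rank-sum on change | t-test on change | ANCOVA | CI half-width, change → ANCOVA |
|---|---|---|---|---|
| 0.3 | 0.371 | 0.393 | 0.537 | 0.93 → 0.77 |
| 0.5 | 0.492 | 0.518 | 0.620 | 0.79 → 0.69 |
| 0.7 | 0.700 | 0.730 | 0.784 | 0.61 → 0.57 |
| 0.9 | 0.991 | 0.993 | 0.993 | 0.35 → 0.35 |

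Other settings, rank-sum on change → ANCOVA:

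| Setting | ρ = 0.3 | ρ = 0.5 | ρ = 0.7 | ρ = 0.9 |
|---|---|---|---|---|
| 10 v 20, 0.5 SD | 0.174 → 0.248 | 0.226 → 0.296 | 0.344 → 0.405 | 0.767 → 0.799 |
| 8 v 16 (scans missing), 0.8 SD | 0.294 → 0.442 | 0.381 → 0.509 | 0.587 → 0.676 | 0.964 → 0.976 |
| 10 v 10 (one tailored arm v PVI), 0.8 SD | 0.268 → 0.410 | 0.361 → 0.480 | 0.530 → 0.623 | 0.946 → 0.961 |

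**Step 3: chance imbalance.** At 10 v 20 the baseline difference has SD √(1/10 + 1/20) = 0.387σ. A difference beyond 0.5σ in either direction is 0.5/0.387 = 1.29 standard errors, so its probability is 0.197. Given a 0.5σ imbalance, the change-score estimate is shifted by (1 − ρ) × 0.5σ: 0.35, 0.25, 0.15 and 0.05σ.

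**Step 4: the pre/post t-test.** This matters only if the test were run unpaired. With n = 30, a 0.4 SD decline and ρ = 0.5, power is 0.562 paired and 0.275 unpaired (40,000 replicates).

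**The case against.** **The plan does not rule out adjustment.** Section 7b speaks only of an association. Section 7a uses the same term for time to recurrence, which section 7c then analyses with univariate and multivariate Cox models. The rank-sum sentence is not tied to strain by name. This stands in part: an adjusted strain model is not excluded. But none is planned, and the rank-sum test is the only between-arm method named that fits the outcome. Leaving the choice until the data are in hand is what pre-specification should prevent.

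**The power comparison combines two changes.** This is correct. At 0.8 SD and 10 v 20, moving from the rank test to a t-test on change accounts for 0.022 of the 0.166 gain at ρ = 0.3, 0.026 of 0.128 at 0.5 and 0.030 of 0.084 at 0.7. The rest is baseline adjustment.

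**The gain depends on an unknown ρ and on normal data.** This is also correct. The gain is near zero at 0.9 and reverses above about 0.92. But the possible loss is about 1% of variance at 0.95, against a gain of about 32% at 0.3. Non-normal data were not simulated, so a rank-based sensitivity analysis is reasonable.

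**The imbalance argument should not be overplayed.** An imbalance above 0.5 SD has a probability of about 20%, so it is a real possibility rather than the expected case. The shift it causes is the same inefficiency as in the variance ratio, seen conditionally, and not a second cost.

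**It is a secondary outcome in a small pilot.** ANCOVA power for 0.5 SD is still only 25% to 41% for ρ from 0.3 to 0.7. That limits what the result can show, but it is no reason to discard information already collected.

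**Conclusion.** The concern holds. The planned comparison is valid and unbiased over randomisations, but it leaves baseline strain unused when every patient contributing a change score has it. For ρ between 0.3 and 0.7, ANCOVA removes roughly 12% to 32% of the variance of the arm effect and adds 8 to 17 percentage points of power over the rank-sum test for a 0.8 SD difference at 10 v 20. At ρ = 0.9 the two are practically equal. These sizes rest on assumed correlations, normality and equal SDs, and the power figures also on the assumed effect sizes.

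This is an efficiency improvement that should be made, not a flaw that invalidates the trial. It does not cure the small sample.

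**What to change.** Replace the strain analysis in sections 7b and 7c with wording such as:

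> Left atrial and left ventricular global strain at 1 year will be compared between arms by ANCOVA with baseline strain as covariate, for PVI only against the pooled tailored arms and by arm. This replaces the rank-sum test for strain. Results will be reported as adjusted mean differences with 95% confidence intervals. Regional strain will use the same model with a random patient effect. The number of patients with evaluable baseline and 1-year scans will be given by arm. Pre/post t-tests are paired and descriptive. All strain results are exploratory.

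If change is preferred as the outcome, adding baseline strain as a covariate gives the same arm coefficient, because moving baseline to the other side of the equation alters only its own slope. A rank-based sensitivity analysis can be added for non-normal data.

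The cost is SAP wording and, for global strain, one residual degree of freedom (27 to 26 in the three-arm model; critical t 2.052 to 2.056). The regional model estimates more parameters and was not simulated here. No new data, visits or scans are needed.
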